4.2 Intervention

4.2.1 iEHR

The iEHR intervention consists of an innovative electronic platform for smoking screening and automated smoking cessation support for parents who smoke. Elements of iEHR will be tailored to fit practices' workflow, staffing, resources, and physical configuration. The intervention involves training all office staff to utilize the iEHR system to assist all parents who smoke to support sustainable workflows and reduce the clinician burden. Components of the iEHR will include:

(1) Identification of smokers and self-assessment of quitting preferences: Screening for parent smoking in the intervention arm will be expanded upon using the iEHR pre-visit screening questionnaire (Appendix 5). The final wording and look of the questionnaire may be updated when the technical team will start integrating it in the EHR. Parents will complete the questionnaire prior to their visit with the clinician, either via MyCHOP prior to the office visit or on a tablet or their own device once they arrive to the office. All parents will receive this pre-visit screening questionnaire. We will determine the appropriate frequency of the screener, so that it's not burdensome to the parents and does not disrupt practice workflow. This workflow, which is already occurring and accepted widely, enhances the role of front desk staff to ensure that clinical information is available in the chart prior to the visit with the clinician.

(2) Counseling: Upon review of the pre-visit screener results, the iEHR will automatically document a parent's intention to quit and services requested to help them quit and suggest motivational messages to increase parents' acceptance of services.

(3) Automatically generated prescription for NRT/NRT delivery: the iEHR will automatically generate a prescription for NRT for parents who smoke (unless they opt out of receiving the prescription), including for those cutting down to quit as recommended in latest guidelines.³⁸ Prescriptions for two forms of NRT (patch and gum) will be printed. Based on information available in the EHR for the parent who completed the pre-visit screening questionnaire, all identifying fields for the prescription will be populated. Prescriptions will be either handed over to the parents or faxed/electronically transmitted to their pharmacy or NRT will be mailed/delivered to them. We may use the services of the company called, BrightMedical, to facilitate the delivery of the NRT medication to families.

(4) Automated Quitline and SmokefreeTXT enrollment:

In the CEASE pre-visit screening questionnaire (Appendix 5), smoking parents will be offered automatic enrollment in the state's free tobacco Quitline and the SmokefreeTXT program, a text message program offered by the National Cancer Institute.

4.2.2 Community Health Navigators (CHNs)

Table 2. Community Health Navigator role

CHN session	Ask ²⁵ (Assessment)	Assist (Counseling)	Assist (Care coordination)	Refer (Resources)
1	Identify all household tobacco users 
 • Readiness to quit • Smoke-free home & car rules • Previous quit attempts • NRT insurance coverage • Identify pharmacy 	Enhance intervention content: 
 • Quit smoking tools & techniques for all tobacco users • Thirdhand smoke • Set quit date 	
 • Ensure connection to Quitline • Ensure NRT access at local pharmacy • Communicate with child's clinician & if possible, parents' clinician about household smoking status using iEHR 	Follow-up to ensure resource awareness & receipt of: 
 • NRT scripts • Quitline • SmokefreeTXT
2	
 • Reassess motivation and progress • NRT script filled • Connected with Quitline/ local cessation resources • Assess smoke-free zones 	Reinforce intervention content and all of the above	
 • All of the above 	
 • Develop strategies to overcome barriers to service receipt

Parents in the intervention arm will also be offered the additional support of CHOP CHNs (Appendix 11). CHNs are employees of CHOP Community Asthma Prevention Program (CAAP) led by the co-PI of this study [name]. CHNs are listed on the CHOP study team and when additional CHOP CHNs are hired for this study, they will be added to the study team. CHNs will work with offices to provide customized smoking cessation support to household tobacco users through phone follow-up, ensuring access to medications and services, and/or home visits, depending on the needs of each family and as study resources allow (Table 2). Home visits could be virtual if there are in-person visit restrictions due to COVID-19.

The CHN will contact the smoker within approximately one week following enrollment to set up the first telephone, video, or in-home session, if they are interested. At the first session, the navigator will discuss various types of services available and work with the smoker to determine their best cessation plan. The CHN will ask smokers to set aside up to 1 hour for the session. The second session will be scheduled for approximately 2-4 weeks later, depending on need and availability. After the first session, the CHN will make phone calls or texts to review progress of cessation activities, offer support, and connection to resources. After the second session, these calls will occur as needed for 1 year. The CHN will document any contact made in a standard EHR patient outreach encounter that will be sent to the child's clinician. Using the EHR, clinicians will also be able to message the CHN.

Depending on parent preference, a session could include a telephone or video call with the CHN or home visit, if requested. Home visits could be virtual if there are in-person visit restrictions due to COVID-19.

4.3 Follow-up

4.3.1 Parent Follow-up

For smoking parents in the longitudinal cohort (See Figure 1), 12-month follow-up in-person/remote survey (Appendix 6), and biochemical validation of self-reported 7-day abstinence will be obtained using proven protocols to collect the samples in-person at the practice or by using remote survey and mail-in cotinine swabs for parents not present at the practice.

- Cotinine levels will be measured for all parents who reported quitting smoking
- In addition to the cotinine test, parents who report current use of NRT or e-cigarettes or have cotinine levels ≥ 10 ng/ml will have the option to get carbon monoxide levels tested to confirm combusted tobacco abstinence.
 - For in-office follow ups (see below for more details), to prevent missing parents who might be eligible for carbon monoxide test, we may ask parents who report current use of NRT or e-cigarettes to get their carbon monoxide levels tested in-office without knowing their cotinine levels yet. We will use their carbon monoxide test readings only if their cotinine levels are ≥ 10 ng/ml (we will get the cotinine results from the lab).

The enrolled parent will be eligible for the 12-month follow-up, about three-weeks before their 12-month study enrollment date. We will deploy several strategies to maximize follow-up efforts.

We will generate rosters of enrolled parents due for their 12-month follow up, who have an upcoming visit scheduled during the follow-up window. These reports will be regularly updated to reflect newly scheduled appointments.

Enrolled parents eligible for follow-up will complete the follow-up assessment in one of the following three ways:

1. **Follow-up via text/email/portal message(myCHOP):** Parents who consented to texting on the baseline Parent Enrollment Survey (Appendix 4) may be texted a follow up survey link. Participants may receive several text reminders to remind the parent to complete the follow up survey. Parents may also be sent the follow up survey link by email or through portal messaging (myCHOP).

If the parent completes the survey via text, email, or myCHOP, and is eligible for the cotinine swabs and CO test, the last page of the survey will notify them that they

should expect to receive a pre-paid mail envelope with the swab collection kit and a CO test monitor and that we may follow up via phone calls/text/email/myCHOP with additional instructions. If the parent has not mailed their salivary cotinine swab kit or not uploaded their CO readings (if eligible), then, we may approach them at the practice in-person at any upcoming appointment to complete the pending assessments.

If the parent hasn't completed the follow-up survey in-person or remotely and the 12-month follow-up date has passed and there is no scheduled appointment in the next couple of months, we may continue to try to follow-up with the participant remotely.

2. **In-office follow-up:** At the participating CHOP primary care sites, study team may approach eligible enrolled parents whose visit falls during the follow up period window. To maximize opportunities for follow up, if the parent has a scheduled visit at any CHOP locations (e.g., CHOP specialty care), the study team may also approach parents that haven't completed follow up procedures at that CHOP location. The study team will first ask for parent's permission to conduct follow up at that CHOP location. Only if the parent feels comfortable, the study team will proceed with follow up.

The study team will complete the follow-up survey and if the parent is eligible will offer the cotinine swabs and carbon monoxide breath tests for in-person completion. If not mailed to the lab immediately, the cotinine tests may be stored in a secure location at the corresponding primary care site or at the study team's CHOP office (Roberts) until they are mailed to the lab by the study team.

3. **Phone follow-up:** The study team may call parents to complete their follow-up survey remotely. During the call, the study team member will briefly remind participants of their enrollment, and the purpose of the call before completing the follow-up survey. If the study team is not able to get in touch with the subject via phone, they may send them one or more postcards to remind them of their study participation and encourage them to call/text back to complete the follow-up survey and get their incentive. The study team may also look for updated contact information of the parent in the child's medical record.

If the parent completes the survey remotely via phone and is eligible for the cotinine swabs and CO test, the last page of the survey and the study team member will notify them that they should expect to receive a pre-paid mail envelope with the swab collection kit and, if eligible, a CO test monitor. They will also be told that they may receive a follow up phone calls/text/email/portal message with additional instructions after the kits have been mailed. If the parent has not mailed their salivary cotinine swab kit or not uploaded their CO readings (if eligible), then, we may approach them at CHOP in-person at any upcoming appointment to complete the pending assessments.

4.3.2 Ongoing EHR Documentation & Evaluation

The EHR documentation of screening and services delivery fidelity, will be ongoing throughout the study before and immediately following implementation, 6, 12, 18, 24, 30, and 36 months. This data is not available from the longitudinal cohort as it requires an assessment of care provided at the practice-level. Specifically, we want to know what services are being delivered at the follow-up time period in the practice overall (as opposed to the limited subset of the practice that it is in the longitudinal cohort).

4.3.3 Practice Clinicians and Staff Qualitative Interviews

In-depth qualitative interviews will be conducted with clinicians and key staff from the intervention practices 6-weeks following implementation and at 12, and 24 months. Clinicians and clinical staff may be recruited for qualitative interviews via e-mail, referral from a colleague, flyer or through a personal solicitation. Prior to the interviews, participants will be offered an information sheet (Appendix 2). The interview guide (Appendix 7) will be based on questions from RE-AIM tools and the CFIR (Consolidated Framework for Implementation Research) interview guide. The interview will be conducted to collect data on the factors that influence intervention implementation. We will also use data from the interviews to improve implementation and sustainability through tailoring the intervention.

The interview process will follow a standard procedure, which is outlined as follows:

Intervention Practice Respondents:

- As a condition of participation in the study, clinicians and staff who will complete the qualitative interviews will complete consent forms (Appendix 8).
- Interviews will be scheduled with selected clinicians and staff at intervention practices. These selected clinicians and staff we expect to include the practice champion and the administrative staff member most involved in the implementation of the intervention; other interviews may be scheduled, if the practice has capacity for additional interviews.

The interviews will be conducted in person, by phone, or HIPPA-compliant video conferencing. The qualitative researcher conducting interviews will begin each interview by asking permission to record, outlining the purpose of the interview, describing the rights of respondents to stop the interview or recording at any time, and giving a brief explanation of how interview data will be used. Interviews will only be recorded with permission.

Recordings will be uploaded to the transcription service provider (ADA Transcriptions). ADA Transcriptions is a HIPAA-compliant, full-service transcription company specializing in medical and academic research. Additionally,

CHOP has a Master Business Associate agreement with the ADA Transcription. The audio-recordings will be uploaded and temporarily stored on ADA Transcriptions online platform that is encrypted and HIPAA compliant. ADA Transcriptions will de-identify and complete the transcriptions and provide each audio-recording and transcription a filename and password-protect it. The password protected transcriptions will then be securely transferred to the designated research team listed on the online platform system. Only designated CHOP and MGH study team staff will be given access to transcriptions. The interview data will be used anonymously in conference presentations, articles, and reports. As part of the rapid-response quality improvement, data will also be used to improve the intervention and address factors that influence implementation of the intervention.

4.4 Subject Completion/Withdrawal

Parents may withdraw from the study at any time without prejudice to their care. It will be documented whether or not each subject completes the clinical study. If the Investigator becomes aware of any serious, related adverse events after the subject completes or withdraws from the study, they will be recorded in the source documents and will be reported as an adverse event to the IRB.

Clinicians and clinical staff can withdraw their participation from the interviews at any time without specific reason.

4.4.1 Early Termination Study Visit

For the intention to treat analysis, any parent who withdraws or drops out of the study will be considered as a smoker.

5 STUDY EVALUATIONS AND MEASUREMENTS

5.1 Screening and Monitoring Evaluations and Measurements

5.1.1 Medical Record Review

The following variables will be abstracted from the EHR to measure the sustainability of the intervention. The relevant domains the items address are listed parenthetically:

- Parental smoking status (Ask)
- Child's tobacco smoke exposure at home (Ask)
- NRT prescription given/referred to BrightMedical (Advise and Refer)
- Referred to the Quitline (Refer)
- Referred to the SmokefreeTXT program (Refer)
- Other smoking or vaping related information collected in the EHR
- Parent and child health and demographic characteristics (e.g., child's insurance status, child's race/ethnicity, child's age, as well as all diagnosis, treatment, updated contact information and health care services utilization)

5.1.2 Laboratory Evaluations

- Salivary cotinine swab will be taken from parents who report quitting smoking at the 12-month follow-up time period. The participant's Study ID number will be used to identify saliva samples sent to the laboratory for the cotinine analysis. No identifying information will be given to the testing laboratory.
- Parents who reported using NRT or e-cigarettes or have cotinine levels ≥ 10 ng/ml will have the option to get carbon monoxide levels tested to confirm combusted tobacco abstinence, to confirm self-reported smoking cessation. We will ensure that we utilize the leading infection control technologies and practices for any sample collection.
 - For in-office follow ups, to prevent missing parents who might be eligible for carbon monoxide test, we may ask parents who report current use of NRT or e-cigarettes to get their carbon monoxide levels tested in-office without knowing their cotinine levels yet. We will use their carbon monoxide test readings only if their cotinine levels are ≥ 10 ng/ml (we will get the cotinine results from the lab).

5.1.2.1 *Laboratory Evaluations*

1. Cotinine

To confirm cessation at 12 months, parents will complete a salivary cotinine specimen either collected in the clinic with a study team member or collected remotely. In the latter case, collection will be performed in front of study team member via a live-video conference, whenever possible.

- Subjects will use a salivary swab measurement that they are able to perform on their own that needs to be mailed to the study team/lab after sample collection.
- This will be performed either in front of a study team member at the primary care clinic or in front of a study team member via a video-conferencing session, if possible. No videos will be recorded. The specimen will be mailed by the respondent in a pre-stamped envelope to the lab.

We will use a feasible system for salivary cotinine collection that enables study participants to easily obtain their own saliva sample and does not require refrigeration. The obtained saliva samples will be sent to laboratory for cotinine testing. The RA will explain the procedures in detail before and after obtaining the cotinine swab. The sample will be

obtained in a quiet, discreet manner in the most private location possible in the practice/CHOP setting. Samples will be subsequently sent to laboratories for analysis. The laboratory will send the results via email to the study staff. If requested by the parent, the results of the cotinine test will be shared with them. Parents who will consent and provide the sample will be given a \$50 incentive. The sample will remain anonymous by identifying it with the parent's study ID number.

Parents who do not have a return annual visit or a follow-up visit during the follow-up time-period (or if there are in-person visit restrictions due to COVID-19), may be contacted remotely for the 12-month survey; parents reporting 7-day abstinence will receive a saliva collection kit with instructions by mail. When possible, saliva sample collection will be performed in front of study team member via a live-video conference call. No videos will be recorded.

2. Carbon monoxide (CO)

In this study, in addition to the cotinine test, parents reporting 7-day abstinence and who also report current use of NRT or e-cigarettes or have cotinine levels ≥ 10 ng/ml will have the option to get carbon monoxide levels tested to confirm combusted tobacco abstinence. The breath CO test is non-invasive and an easily administered test. RAs will obtain breath samples from all eligible parents who agree to be tested using breath CO monitors.

For in-office follow ups, to prevent missing parents who might be eligible for carbon monoxide test, we may ask parents who report current use of NRT or e-cigarettes to get their carbon monoxide levels tested in-office without knowing their cotinine levels yet. We will use their carbon monoxide test readings only if their cotinine levels are \geq /ml (we will get the cotinine results from the lab).

CO breath levels will be measured using the CO breath analyzer according to the manufacturer's recommendations. Parents will be asked to hold their breath for 20 seconds and then exhale slowly and fully into the mouthpiece of the instrument during which CO breath was recorded. The CO breath levels are given in parts per million (ppm). The device will be calibrated according to the manufacturer's instructions prior to use. For CO confirmed quitting, expired-air CO cutoff level of < 5 ppm will be considered quit.

The single use mouthpieces are individually wrapped for ease of handling and greater infection. Mouthpieces will be replaced after every use or an individual device will be used per parent. The wipes provided with the breath monitors have been tested by the supplier and found effective against (COVID-19/SARS-COV-2), as the product shows efficacy against feline coronavirus, a surrogate coronavirus (for COVID-19/SARS-COV-2).

Those parents who do not have a scheduled visit during the follow-up time-period, may be contacted remotely for the 12-month survey; parents reporting 7-day abstinence and on NRT or e-cigarettes, or who have a cotinine level of ≥ 10 ng/ml will be offered to get carbon monoxide levels tested to confirm cessation. They will receive a CO monitor in the mail with instructions. The results can be uploaded in real-time by the parent via a smartphone app and when possible, breath test will be performed in front of study team member via a live-video conference call. If a parent does not have a smartphone, they will be able to communicate the results back via a call or text to a study team or any other communication approach that is most convenient to them.

For remote follow ups, to minimize the burden of data collection, we will aim to send the CO monitors to eligible parents after we get their cotinine results back. If this strategy impedes the collection of CO readings, we may consider sending the CO monitors and cotinine kits simultaneously but will still use the CO readings only if the cotinine level is ≥ 10 ng/ml.

Parents who will consent and provide the breath sample (in the clinic or remotely) will be given a \$50 incentive. They will be compensated for CO test completion regardless of whether their CO reading will be used.

5.1.2.2 *Table: Clinical Laboratory Tests*

Category	Tests
Smoking Cessation Testing	1. Saliva Cotinine Test 2. CO Breath Test

5.2 Efficacy Evaluations

Below is the complete list of all outcomes that will be collected and evaluated throughout the study.

Table 3: Main Outcomes Measurement

Outcomes	Operational Definition and Assessment Method	Sources for Construct	Timing
Parents' combusted tobacco quit rates, and tobacco free behaviors	Assessed by exit or telephone survey of parents [longitudinal cohort]		
7-day abstinence (Primary Outcome for Aim #1)	% of parental smokers who have 7-day abstinence (biochemically verified at 12-months)	BRFSS ⁴² ; NHIS ⁴³	12-months post initial visit
Quit attempts	% of parental smokers who report at least one 24-hour quit attempt since pediatric visit	BRFSS ⁴² ; NHIS ⁴³	12-months post initial visit
Use and Duration of pharmacotherapy	% of parental smokers who report use of gum or patch since pediatric visit and duration of use	[name] et al. ⁴⁴	12-months post initial visit

Institution of smoking bans	% of parental smokers who report strict smoke-free and e-cigarette free home and car rules	Drehmer et al. ¹⁸ [name] et al. ^{44,45} Emmons et al. ⁴⁶ Bauman et al. ⁴⁷ Ossip et al. ²³ Nabi-Burza et al. ⁴⁸	12-months post initial visit
Establish the incremental cost per quit of the intervention compared to usual care control	Assessed by observation and survey of personnel		
Health care system costs: time use of IT personnel, CHN, clinician, practice staff, and training personnel	Total time devoted to intervention activities using the direct observation log (Appendix 9) multiplied by national average wage rate for each type of personnel	Neumann et al., ⁴⁹ Bureau of Labor Statistics ⁵⁰	Prior to initial visit, 12- and 24-months post initial visit, direct observation log, navigator logs
Societal costs (exploratory): Parent costs (parent time, parent out-of-pocket costs for medication), Quitline costs, medication costs	Total parent time devoted to intervention/usual care activities multiplied by national average wage rate by age; published data for Quitline and medication costs ^{51,52}	Neumann et al. ⁴⁹ Bureau of Labor Statistics ⁵⁰	Prior to initial visit, 12- and 24-months post initial visit, navigator logs
Assess delivery and sustainability of interventions	Assessed by 12-month follow-up survey of parents, iPad screener, EHR data documentation and key informant interview		Parental 12-month follow-up survey.
Delivering cessation assistance	% of parental smokers who received at least one of the following 1. prescription of pharmacotherapy or 2. referral to Quitline or SmokefreeTXT	HEDIS measures; ⁵³ [name] et al. ^{44,54,55}	Pre-visit screener data, EHR data documentation before and immediately following implementation, 6, 12, 18, 24, 30, and 36 months post implementation
Screening for parental smoking	% of all parents seen in practice who are screened for smoking status using the screener data	HEDIS measure ⁵³	
Advising parents to quit	% of parental smokers advised to quit smoking	HEDIS measure ⁵³	
Counseling parents about rules	% of parental smokers counseled about strict smoke-free and e-cigarette free home and car rules	Drehmer et al. ¹⁸ [name] et al. ⁵⁶	
Implementation and sustainability factors	Clinician and key staff member assessment of practice change resulting from the intervention	CFIR interview guide ⁵⁷ ACIC, ⁵⁸⁻⁶⁰ PSAT, ^{59,60} IMPROVE ^{61,62} , RE-AIM ⁶³	6-weeks following implementation and at 12 and 24 months

5.2.1 Diagnostic Tests, Scales, Measures, etc.

The list of tests and measures is provided above.

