6.4 Sample Size and Power

Sample size calculations are based on having at least 8 practices with a minimum of 5 clinicians per practice. Clinically important and conservative estimates of validated 12-month quit rates based on prior studies are 13.8% in the iEHR + Navigator group and 7% in the usual care control group. These estimates are based on the worst-case scenario from prior studies where all enrolled parents lost to follow-up were assumed to be smokers at 12-month follow-up. The effective sample size needed for the primary outcome accounts for clustering at the clinician and practice level (4 practices per arm x 5 clinicians per practice) with intra-class correlation of .014 calculated from our previous research. By enrolling approximately 100 parents in each practice (400 per arm), we will have 80% power for the primary outcome (iEHR + Navigator vs. usual care control). Effect sizes for outcomes other

than cessation will likely be much greater; the study will have adequate power to detect these differences, shown in our prior studies.

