2. Establish the incremental cost per quit of intervention. The healthcare system's perspective is central to establishing the interventions' disseminability and sustainability. As a secondary analysis, we will consider costs from a societal perspective to pave the way for future cost-utility analyses. We will calculate the incremental cost per quit of the iEHR+Navigator intervention relative to usual care, as we have done in prior studies: $(\text{Total cost at 12 months}_{\text{arm[i]}} - \text{Total costs}_{\text{arm[j]}}) / (\text{Total biochemically confirmed quits at 12 months}_{\text{arm[i]}} - \text{Total biochemically confirmed quits at 12 months}_{\text{arm[j]}})$. Development costs for iEHR will not be included in primary analyses as the iEHR will be fully developed and ready for dissemination by the time the intervention begins. Direct costs include iEHR set-up, customizing, implementing, and sustaining the systems changes that support service delivery and cessation, electronic tablets, and related clinician work. Direct costs further include: the CEASE intervention staff time to support the practice leader and the time clinicians and office staff take to learn and use the online module. Time use will be tracked by administrative records, direct observation by the RA, and surveys. For the iEHR+Navigator arm, we will create a log to note the types of CHN outreach efforts, time spent, and the type of services delivered to smoking parents. Personnel costs will reflect national average wages for each personnel type. We will use Monte Carlo simulation methods to develop confidence bounds on our cost-per-quit estimates. Following standard methods of economic evaluation in prior studies, we will also perform parameter-specific sensitivity analyses in which individual parameters are varied singly and in combination, through plausible ranges to assess the relative impact different elements of the program have on overall cost-effectiveness.

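### Staff time is priced at the national average wage with no employer-paid benefits or payroll taxes, so the personnel part of the health-system cost per quit is too low if the rule is applied as written

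*Protocol*

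**What the plan says.** The incremental cost per quit is a named secondary objective. SAP secondary outcome 2 defines it as the between-arm difference in 12-month costs divided by the difference in biochemically confirmed quits. Its stated viewpoint is the employer's side: "The healthcare system's perspective is central to establishing the interventions' disseminability and sustainability". A societal analysis is secondary.

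The unit price of staff time appears twice. In Protocol section 5.2, Table 3, the row "Health care system costs: time use of IT personnel, CHN, clinician, practice staff, and training personnel" is measured as time spent on intervention activities "multiplied by national average wage rate for each type of personnel". The SAP agrees: "Personnel costs will reflect national average wages for each personnel type". Table 3 cites the Bureau of Labor Statistics but names no data series.

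No passage mentions benefits, payroll taxes, total compensation or a loading factor. The SAP's list of direct costs is wider than the Table 3 row: it covers system set-up and maintenance as well as "electronic tablets, and related clinician work". Its sensitivity analyses are described generally, as "parameter-specific sensitivity analyses in which individual parameters are varied singly and in combination", without naming wages or a loading.

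**The concern.** A health system deciding whether to adopt the programme would have to budget for what it pays per hour of staff time. That is the wage plus employer-paid benefits and payroll taxes. Protocol section 4.2.2 leaves no doubt about who bears this for the navigators: "CHNs are employees of CHOP Community Asthma Prevention Program". The missing amount does not enter through the hours either, because Table 3 counts only time given to intervention activities.

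The omission would not cancel between arms. Navigator sessions and calls are offered only in the intervention arm, and training all office staff on the iEHR belongs to the intervention (Protocol sections 4.2.1 and 4.2.2). Most of the unpriced cost therefore sits on one side of the numerator, and the resulting bias favours the intervention. What is at stake is the figure meant to inform dissemination and sustainability.

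**Working it through.** The documents give no wage, loading, personnel share or cost per quit, so there is no stated cost figure to reproduce. The direction follows from the formula; the size needs assumptions.

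**Inputs from the documents**
- Unit price of staff time: national average wage (Protocol Table 3; SAP secondary outcome 2).
- Planned quit rates: "13.8% in the iEHR + Navigator group and 7% in the usual care control group" (Protocol section 6.4).
- Parents per arm: about 400 (Protocol section 6.4).

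**Assumed inputs, not in the documents**
- f, employer-paid loading as a fraction of wages, averaged over personnel types: 20% to 40%.
- s, personnel share of the wage-only incremental cost: 50% to 100%. Table 3's health-system row lists personnel time only, which would give 100%; the SAP adds tablets and set-up items, which may bring it lower.

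**Step 1: denominator.** Incremental quits = 400 × (0.138 − 0.07) = 27.2. The pricing rule does not change this.

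**Step 2: effect on the ratio.** With wage-only incremental cost C, the personnel part is sC and the omitted amount is f × sC. Hence

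loaded cost per quit ÷ planned cost per quit = (C + f·s·C) ÷ C = 1 + s·f,

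and the share of the loaded figure that is missed is s·f ÷ (1 + s·f).

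| f | s = 50% | s = 75% | s = 100% |
|---|---|---|---|
| 20% | 1.10 (9.1% missed) | 1.15 (13.0%) | 1.20 (16.7%) |
| 30% | 1.15 (13.0%) | 1.225 (18.4%) | 1.30 (23.1%) |
| 40% | 1.20 (16.7%) | 1.30 (23.1%) | 1.40 (28.6%) |

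**Step 3: illustration.** For each $100,000 of wage-only incremental cost, the planned figure is 100,000 ÷ 27.2 = $3,676 per quit. Loaded, it is 110,000 ÷ 27.2 = $4,044 at f = 20%, s = 50%, and 140,000 ÷ 27.2 = $5,147 at f = 40%, s = 100%. The $100,000 is a scale only, not an estimate of the trial's costs.

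**Step 4: direction.** The factor exceeds 1 whenever f > 0 and the intervention arm uses more staff time than usual care. The second condition is implied by the design, though the documents give no hours.

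**The case against.** *The documents name wages but never exclude benefits.* The wage source is cited without a series, and the SAP says the ratio will be calculated as in the team's prior studies, so a loading might be applied in practice. This stands as a limit on certainty. A reader might infer that the reported figure is bound to be understated; the documents support only that it will be if the written rule is followed. If a loading is intended, the text should say so.

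*Table 3 exaggerates the personnel share.* This also stands. A reader might take the Table 3 row to mean that the understatement passes into the cost per quit almost in full, giving a factor of 1.2 to 1.4 on the whole outcome. That range belongs to the personnel part alone. The SAP's direct costs include tablets and set-up items, and no personnel share is stated.

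*The sensitivity analyses and Monte Carlo bounds already cover it.* Only in part. The parameters to be varied are unnamed, and varying inputs around a low base case does not correct that base case.

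*The consequence is small.* This is a secondary outcome with no stated cost-per-quit threshold to cross, and the denominator is imprecise. With 400 ÷ (4 × 5) = 20 parents per clinician, the design effect is 1 + 19 × 0.014 = 1.266. The standard error of incremental quits is then √[400 × 1.266 × (0.138 × 0.862 + 0.07 × 0.93)] ≈ 9.7, for a 95% interval of about 8 to 46. That bears on priority. It does not excuse a one-directional error that can be removed by rewording.

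*National averages help generalisability and comparison with earlier work.* Agreed; the average can stay national and simply be one of compensation. Wage-only costing can still be reported alongside it for comparison.

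**Conclusion.** The point holds in a limited form. The written price is the wrong one for the perspective that the SAP calls central, and this is more than a missing detail because both documents state the same rule. Applied as written, it lowers the personnel part of the health-system incremental cost per quit, mainly through the intervention arm.

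The loaded figure would be 1.10 to 1.40 times the planned one, so the planned figure would miss 9.1% to 28.6% of the loaded cost. This rests on the assumed f and s and on the intervention arm using more staff time; the documents cannot narrow it. Non-labour costs, the count of quits and the primary comparison of quit rates are untouched.

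**What to change.** In Protocol Table 3 and SAP secondary outcome 2, replace the national average wage by *national average hourly compensation (wage plus employer-paid benefits and payroll taxes)* for each personnel type. Name the data series and year in both places. Report wage-only costing as one of the parameter-specific sensitivity analyses already planned.

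The cost is a wording change in two places and one published multiplier per personnel type. Time logs and surveys are unchanged and no new data are collected, so it can be done at any point before costs are analysed. The downside is a somewhat less favourable cost per quit.
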